#### 4. Background and Rationale:

Total laparoscopic pancreaticoduodenectomy (TLPD) remains one of the most advanced laparoscopic procedures. Owing to the evolution in laparoscopic technology and instrumentation within the past decade, laparoscopic pancreaticoduodenectomy is beginning to gain wider acceptance.(1)

Gagner and Pomp were the first to describe the laparoscopic Whipple procedure in 1994. The long operative times and technical difficulties coupled with the need to develop advanced laparoscopic skills were valid reasons that supported the initial reluctance to pursue these sophisticated minimally invasive operations. Recently, laparoscopic pancreaticoduodenectomy has started to gain wider acceptance as surgeons become more comfortable with laparoscopic technology. As a result, TLPDs have been reported with an increased frequency from institutions internationally.(2-15)

In recent years, total laparoscopic pancreaticoduodenectomy (TLPD) has been introduced as a feasible alternative to open pancreaticoduodenectomy (OPD) when performed by experienced surgeons in laparoscopic and pancreatic surgery. Its application has been gradually increased, but its safety, reproducibility, and oncological outcomes are still debated due to its technical complexity and prolonged operating time. There are different experiences present in the literature regarding indications, surgical techniques, postoperative outcomes, benefits and limitations of this approach, oncological results, learning curve, and costs. There is no standardized surgical technique for TLPD. Different techniques exist for both the demolitive stage and the reconstructive stage. We summarized the different aspects of the surgical technique based on the various experiences reported by different authors. Compared to OPD, TLPD provides the advantages of laparoscopy, i.e., reduced blood loss, decreased postoperative pain, and shorter length of hospital stay, without increasing the rate of postoperative complications or compromising oncological outcomes. With increased experience, more challenging cases may also be approached with this technique, including those requiring major vascular resections or multi-visceral resections.(16)

Pancreaticoduodenectomy (PD) has seen improved perioperative outcomes and complication rates over the last few decades (17-20). Nevertheless, it continues to be a morbid operation with complications ranging from 24-59% (21-23). Laparoscopic surgery reduces surgical morbidity in various operations, however laparoscopic pancreaticoduodenectomy (LPD) is a relatively new procedure which lacks a clear consensus regarding its benefits (24-28). Although the first published case was described in 1994, it has been slow to gain popularity (29). This is likely in part due to the challenging technical aspect of the procedure including the retroperitoneal location of the pancreas, close vicinity to the superior mesenteric artery and vein, portal vein and hepatic arteries and the technical difficulty of three anastomosis. In recent years, however, we have seen an increasing

Cairo University

KASR ALAINY

CAIRO UNIVERSITY - FACULTY OF MEDICINE

number of studies examining LPD. Initial research evaluated feasibility and outcomes, assessing whether LPD could be done with adequate safety (30-37). The question then moved to compare to the open approach questioning if it will appreciate the same benefits of other laparoscopic surgeries. Partially enabled by higher volumes at specialized centers, studies began comparing LPD with (OPD). Although there are a handful of pancreaticoduodenectomy review articles evaluating LPD in the literature, many include papers with limited sample sizes and case reports. Our goal in this study is to compare and contrast the outcomes of both approaches aiming to reduce post operative morbidity and oncological outcomes.

## 5. Objectives:

The study aims to determine the advantages and disadvantages of performing total laparoscopic pancreaticoduodenectomy over the open approach and to compare the outcomes aiming to reduce the magnitude of operative morbidity.

## 6. Study Design:

Prospective comparative randomized clinical study

- **Study Methods**

- **Population of study:**

Patients presenting to KASR ALAINY hospital requiring pancreaticoduodenectomy

- **Study location:**

KASR ALAINY Hospitals – Cairo University

- **Inclusion criteria:**

- Patients presenting with pancreatic head tumours, cholangiocarcinoma, duodenal tumours (1st, 2nd and 3rd part) and ampullary tumours who are fit for either open or laparoscopic pancreaticoduodenectomy

- **Exclusion criteria:**

- Patients who are deemed inoperable due to the presence of metastases

- Patients with irresectable tumours

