**- Methodology in details:**

- Patients will present to the outpatient clinic of KASR ALAINY hospitals with pancreatic head tumours, cholangiocarcinoma, duodenal tumours (1st, 2nd and 3rd part) and ampullary tumours who are fit for either open or laparoscopic pancreaticoduodenectomy.
- Full assessment will be done by clinical examination, radiological assessment in the form of EUS, CT scan and metastatic work-up, laboratory investigations in the form of tumour markers and tissue biopsy histopathological examination.
- Patients will be classified into frank resectable, borderline resectable (defined as pancreatic head masses larger than 4 cm in size, equivocal findings of ascites and metastases on CT scan and signs of advanced disease as in marked weight loss and markedly elevated CA19-9 > 1000) and frank irresectable.
- A decision will be made by the multidisciplinary team and patients will be selected to undergo total laparoscopic pancreaticoduodenectomy or open pancreaticoduodenectomy through a randomized manner
- Patients with tumours classified as borderline resectable tumours will be subjected to diagnostic laparoscopy prior to open surgery
- A diagnostic survey and intraoperative ultrasonography were performed to assess for resectability and other pathological conditions such as the presence of ascites, liver metastases and peritoneal deposits and a decision to proceed or abort will be made accordingly.
- Patients classified as borderline resectable will undergo an intraoperative ultrasound assessment of the vessel involvement, LNs and tumour size if irresectability is suspected.
- Open approach will entail a roof top incision
- Laparoscopic approach will entail trocar placement at the following sites:
  - 10 mm visual port at the level of the umbilicus
  - 12 mm port in the right mid-clavicular line 2 cm below the umbilicus
  - 5 mm port in the left mid-clavicular line 2 cm below the umbilicus
  - 5 mm port in the right mid-clavicular line 2 cm above the umbilicus
  - 5 mm port in the left mid-clavicular line 2 cm above the umbilicus
  - An optional 5mm port in the epigastric region if required
- Total internal stents will be placed inside the pancreatic and biliary anastomoses. The size of the stents will be determined according to caliber of pancreatic duct and common bile duct.
- Operative time will be calculated in minutes starting from skin incision to skin closure

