**9- Study outcomes:**

- **Primary outcome:**

- o Operative time
- o Assessment of early post-operative complications including: pain, respiratory complications (collapse, pleural effusion or pneumonia)
- o Incidence of pancreatic and biliary leakage

- **Secondary outcome:**

- o ICU stay and total hospital stay
- o Patient satisfaction in terms of pain, ambulation, ability to resume daily routine activities
- o Blood loss and need for blood transfusion accordingly

- Wound complications including: infection (early) and incisional hernia/port site hernia (late)
- Pathological assessment in terms of LN harvesting and resection margins (R0 resection or R1)

---

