#### 10- Sample size

The sample size was assessed using the G \* power 3.1.9.4 software (Universities Kiel, Germany). The calculation was based on the study of Ammori et al. [11], which reported a mean hospital stay length of  $4.7 \pm 1.125$  days in the OPD group compared to a respective mean of  $8.9 \pm 5.425$  days in the LPD group. After setting the study power at 80% and  $\alpha$  at 0.05, a minimum of 12 patients in each group were required.

---

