#### 11- Statistical analysis

#### 12- Source of funding:

- No Funding

---

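### Four tumour origins are randomised together and neither allocation nor analysis uses origin: one two-level factor would be a cheap gain in precision, not the repair of a bias

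*Combined protocol and SAP*

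**What the plan says.** Section 6 (Study Design, inclusion criteria) makes four origins eligible together: "Patients presenting with pancreatic head tumours, cholangiocarcinoma, duodenal tumours" (first to third part) and ampullary tumours. The methodology part of the same section lists a work-up with EUS, CT and tissue biopsy ahead of the allocation step, so origin should be known, at least provisionally, when a patient is randomised. It also sets up a resectability grouping: "Patients will be classified into frank resectable, borderline resectable" and frankly irresectable.

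Allocation is to laparoscopic or "open pancreaticoduodenectomy through a randomized manner". No sequence, blocking, stratification or minimisation is described. The heading "11- Statistical analysis" has no text under it, so no covariate is named, and no method of comparison either. Section 10 sets the size: "at 0.05, a minimum of 12 patients in each group were required".

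Section 9 makes operative time and leakage primary. Hospital stay is secondary, as is "Pathological assessment in terms of LN harvesting and resection margins (R0 resection or R1"). Duct calibre appears once, in the operative description: "The size of the stents will be determined according to caliber of pancreatic duct and common bile duct".

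**The concern.** Origin is a natural candidate to predict operative time, node yield, margin status and leakage. That is an assumption: the documents give no origin mix, no results by origin and no statement that origin matters. If it does matter, a trial of about 24 patients has two problems. A noticeable imbalance in case mix is fairly likely, and it would make the one realised result harder to read. Variation that a single term could remove would also stay in the error of every continuous comparison.

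Timing matters. An adjustment term can still be written into the blank analysis section later, but an allocation factor cannot be added for patients already randomised.

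**Working it through.** **The plan's own figure.** Section 10 gives hospital stay 4.7 (SD 1.125) against 8.9 (SD 5.425) days, power 80%, alpha 0.05 and 12 per group. The difference is 4.2; the SD is sqrt((1.125² + 5.425²)/2) = 3.918; d = 4.2/3.918 = 1.072. With a noncentral t distribution, 12 per group has 81.6% power one-sided, so 12 is reproduced. Two-sided, 12 per group has 70.9% and 15 would be needed. The plan does not state sidedness. The two-sided 70.9% is the baseline below.

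**Chance imbalance.** Let K of 24 patients have pancreatic head tumours, with 12 per arm. K is assumed, since the plan gives no mix. The number in one arm is hypergeometric(24, K, 12).

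| K | P(arms differ by 4 or more) |
|---|---|
| 8 or 16 | 0.193 |
| 10 or 14 | 0.214 |
| 12 | 0.220 |

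With an odd K the difference must be odd, so the nearest thresholds are 3 or more (40-41% for K = 9 to 15) and 5 or more (9-10%). Taking all four origins, the chance that at least one differs by 4 or more is 34% for an assumed mix of 12/6/4/2, 43% for 6/6/6/6 and 23% for 14/5/3/2.

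**Validity.** In simulation (20,000 trials per setting, mix 12/6/4/2), the unstratified, unadjusted two-sided t-test had type I error of 4.7-5.2% at R2 = 0, 0.1, 0.2 and 0.3, where R2 is the assumed share of outcome variance explained by origin.

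**One realised imbalance.** Take an 8 v 4 split with K = 12 and no treatment effect. The two origin groups then differ by 2·sqrt(R2) SD, so the arms are shifted by (4/12)·2·sqrt(R2) = 0.21, 0.30 and 0.37 SD at R2 = 0.1, 0.2 and 0.3. Given that split, the unadjusted test rejects in about 7%, 8% and 10% of trials.

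**Precision from one two-level term.** The approximate variance ratio is (1 − R2)·22/21, where 22/21 charges for the lost degree of freedom. The equivalent sample size is its inverse.

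| R2 (assumed) | Variance ratio | Equivalent n |
|---|---|---|
| 0 | 1.048 | x0.95 |
| 1/22 = 0.045 | 1.000 | x1.00 |
| 0.1 | 0.943 | x1.06 |
| 0.3 | 0.733 | x1.36 |

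The 22/21 charge is close to what adjustment costs without stratification. If the factor is also balanced by design, the cost is smaller. With exact balance, two-sided power at d = 1.072 follows from a noncentral t with 21 degrees of freedom and noncentrality 1.072·sqrt(6)/sqrt(1 − R2): 71% at R2 = 0, 75% at 0.1, 80% at 0.2 and 85% at 0.3, against 71% for the plain t-test.

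**What does not work.** Adjusting for four origin levels without stratifying gave 64% power at R2 = 0 and 69% at 0.1, below the 71% baseline. Stratifying without adjusting made the test conservative: type I error 3.7%, 2.8% and 2.1% at R2 = 0.1, 0.2 and 0.3.

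**Leakage.** If leakage differs by 10-20 points between origins (assumed), a 4-patient imbalance shifts the arm difference by (4/12)·10 = 3.3 to (4/12)·20 = 6.7 points. The standard error of the arm difference is sqrt(2p(1 − p)/12): about 12, 16 and 19 points at assumed rates of 10%, 20% and 30%. The shift is therefore about 0.2 to 0.5 of a standard error. The difference detectable with 80% power is 53-55 points.

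**The case against.** The strongest reply is that randomisation already deals with this. Chance imbalance does not bias the comparison on average, the error rate of the plain test stays near 5%, and in roughly four randomisations out of five, for the even values of K above, the arms differ by at most 2 pancreatic head patients. All of this stands. A reader might infer that case mix could drive the leakage or margin result. The figures do not support that for leakage, where ordinary sampling error is far larger than the shift, and the documents give nothing from which to claim it for margins.

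A second reply is that the gain depends on an R2 the documents do not supply. That stands too. It would be wrong to say that precision is lost for nothing: below about R2 = 0.045 the term gains nothing by the approximate formula. What limits this reply is that, with the factor balanced by design, the loss at R2 = 0 is negligible (71% against 71%).

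Third, the blank analysis section and the undescribed randomisation are larger gaps, and an unadjusted analysis is inferred rather than stated. This is fair, but filling the analysis section would not supply an allocation factor.

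Fourth, a reader might think duct calibre should also have been an allocation factor. Nothing shows that it is known before allocation; it is mentioned only for stent sizing. Nor do the documents show that pancreatic head versus other is a better factor than resectability class, which partly overlaps with it through the size criterion for head masses. Hence minimisation on both is an acceptable alternative.

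**Conclusion.** The omission is real and its consequence is modest. Origin is used nowhere in allocation or analysis. At 12 per arm an imbalance of 4 or more pancreatic head patients has a probability of about 19-22% for even counts from 8 to 16 of 24. For continuous outcomes, using one two-level factor in both allocation and model costs almost nothing if origin is irrelevant, and adds about 4 to 14 points of power (71% to 75% or 85%) if it explains 10-30% of the variance. These gains rest on the assumed R2, on the sizing effect for hospital stay carried over as the example, and on close balance within the two strata. This is a cheap improvement in precision and readability. The plan is not biased without it, and for leakage the effect of imbalance is small beside sampling error.

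**What to change.** Before the first allocation:

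- Stratify on one two-level factor, pancreatic head versus other origin, as classified from the pre-allocation work-up, with a separate blocked list for each level. Alternatively, minimise on that factor together with resectability class. Do not use four strata in 24 patients.
- In the statistical analysis section, include the same term in the models for operative time, hospital stay and node count. Do not stratify without adjusting.
- For leakage and margin status, show counts by arm within origin, without a model.
- Report duct calibre by arm as a descriptive variable only.

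The cost is one more allocation list and one degree of freedom. The sample size does not change on this account.

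If patients have already been allocated, the model term and the tables can still be specified before the outcome data are examined, but the allocation part of the gain is lost for those patients. Without stratification the two-level term costs a little more: power at R2 = 0 fell from about 71% to 69% in the simulation.

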**- Methodology in details:**

- Patients will present to the outpatient clinic of KASR ALAINY hospitals with pancreatic head tumours, cholangiocarcinoma, duodenal tumours (1st, 2nd and 3rd part) and ampullary tumours who are fit for either open or laparoscopic pancreaticoduodenectomy.
- Full assessment will be done by clinical examination, radiological assessment in the form of EUS, CT scan and metastatic work-up, laboratory investigations in the form of tumour markers and tissue biopsy histopathological examination.
- Patients will be classified into frank resectable, borderline resectable (defined as pancreatic head masses larger than 4 cm in size, equivocal findings of ascites and metastases on CT scan and signs of advanced disease as in marked weight loss and markedly elevated CA19-9 > 1000) and frank irresectable.
- A decision will be made by the multidisciplinary team and patients will be selected to undergo total laparoscopic pancreaticoduodenectomy or open pancreaticoduodenectomy through a randomized manner
- Patients with tumours classified as borderline resectable tumours will be subjected to diagnostic laparoscopy prior to open surgery
- A diagnostic survey and intraoperative ultrasonography were performed to assess for resectability and other pathological conditions such as the presence of ascites, liver metastases and peritoneal deposits and a decision to proceed or abort will be made accordingly.
- Patients classified as borderline resectable will undergo an intraoperative ultrasound assessment of the vessel involvement, LNs and tumour size if irresectability is suspected.
- Open approach will entail a roof top incision
- Laparoscopic approach will entail trocar placement at the following sites:
  - 10 mm visual port at the level of the umbilicus
  - 12 mm port in the right mid-clavicular line 2 cm below the umbilicus
  - 5 mm port in the left mid-clavicular line 2 cm below the umbilicus
  - 5 mm port in the right mid-clavicular line 2 cm above the umbilicus
  - 5 mm port in the left mid-clavicular line 2 cm above the umbilicus
  - An optional 5mm port in the epigastric region if required
- Total internal stents will be placed inside the pancreatic and biliary anastomoses. The size of the stents will be determined according to caliber of pancreatic duct and common bile duct.
- Operative time will be calculated in minutes starting from skin incision to skin closure

- Blood loss will be assessed in coordination with the anaesthesia team by counting the number of soaked towels and gauze and calculating the amount of blood suctioned throughout the procedure.
- Daily chest assessment to exclude or suspect lung atelectasis, pleural effusion or pneumonia will be done. Further chest imaging will be done if required.
- Daily serial abdominal examination to exclude or suspect pancreatic or biliary leakage will be done. Further laboratory assessment will be done if required (inflammatory markers: TLC, CRP, serum and drain amylase, serum and drain bilirubin), imaging in the form of an abdomen and pelvis CT study may be done if required.
- Daily wound assessment will be done starting 48 hours following surgery
- Pain assessment will be done by means of a visual analogue scale (VAS)
- Early patient satisfaction in terms of post-operative pain, early ambulation, ability to resume daily activities and complications by means of a questionnaire
- ICU stay and total hospital stay will be calculated
- Pathological assessment will be noted in terms of number of LNs harvested and the resection margins (R0 or R1)
- Incision / portsite examination to exclude incisional or portsite hernia.

○ **Does the research involve?**

Human participants

Biological samples/Tissues

Identifiable private data/Information

○ **Type of consent of study participants:**

Written consent

Oral consent

Cairo University

KASR ALAINY  
CAIRO UNIVERSITY - FACULTY OF MEDICINE

No consent needed (Please justify)

o **Potential risks:**

No attributed risks can be related to the study

o **Confidentiality of data:**

All study related information will be stored securely at the study site.

All participant information will be stored in locked file cabinets in areas with limited access.

Participants' study information will not be released outside the study without the written permission of the participant.

Research ethics committee "REC" & Health authorities have the right to review's patient's data

---

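### The plan does not settle whether borderline resectable patients are randomised: routing them to open surgery would confound the comparison with stage, and randomising them without strata leaves chance imbalance at 12 per arm

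*Combined protocol and SAP*

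**What the plan says.** All of the following is in section 6 (Study Design) unless stated otherwise.

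- **Eligibility.** The inclusion criterion admits patients "who are fit for either open or laparoscopic pancreaticoduodenectomy". Metastatic and irresectable cases are excluded.
- **Classification.** Methodology in details sorts patients into frank resectable, borderline and frank irresectable. The middle class is "borderline resectable (defined as pancreatic head masses larger than 4 cm in size, equivocal findings of ascites and metastases on CT scan", together with signs of advanced disease (marked weight loss and a CA19-9 above 1000).
- **Allocation.** After a multidisciplinary decision, "patients will be selected to undergo total laparoscopic pancreaticoduodenectomy or open pancreaticoduodenectomy through a randomized manner". No strata or blocks are named.
- **Borderline patients.** The next bullet reads "Patients with tumours classified as borderline resectable tumours will be subjected to diagnostic laparoscopy prior to open surgery". A later one reads "Patients classified as borderline resectable will undergo an intraoperative ultrasound assessment of the vessel involvement, LNs and tumour size if irresectability is suspected" and names no arm. Between them, a diagnostic survey with ultrasonography, also without a named arm, ends with "a decision to proceed or abort will be made accordingly".
- **Size and analysis.** Section 10 requires at least 12 patients per group. Section 11 (Statistical analysis) has a heading but no text in the version supplied, so no adjustment for class can be seen.

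**The concern.** The allocation bullet covers everyone. The bullet after it mentions a single surgical route for borderline patients, and that route is open surgery. It does not say that it applies only to those allocated to open. A site could therefore read it in two ways:

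- **Reading A:** borderline patients go to open surgery.
- **Reading B:** borderline patients are randomised like the others, and those allocated to open have a diagnostic laparoscopy first.

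The class is defined by mass size and signs of advanced disease. It may plausibly affect operative time (a primary outcome in section 9) and blood loss and resection margins (secondary outcomes), whichever approach is used. If borderline patients gather in the open arm, laparoscopy gains an advantage that does not come from the approach. The question in section 5, the advantages and disadvantages of laparoscopy over open surgery, would then be answered wrongly. This matters more than usual because the arms are so small.

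**Working it through.** **Inputs.** From the documents: 12 per group (section 10), so 24 in total. Not in the documents, hence assumed: the number K of borderline patients, taken as 6, 8 or 12 of 24, and the effect of stage on outcome.

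**The plan's own figure.** Section 10 uses mean stays of 4.7 (SD 1.125) and 8.9 (SD 5.425) days. Pooled SD = √((1.125² + 5.425²)/2) = 3.918, and d = 4.2/3.918 = 1.072. A one-sided t-test at 0.05 gives 12 per group with 81.6% power, which matches. A two-sided test needs 15. Only the arm size of 12 is used below.

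**Reading A.** All K borderline patients are in the open arm, and the arms are assumed to stay at 12:12.

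| K | Open arm borderline | Laparoscopic arm borderline |
|---|---|---|
| 6 | 6/12 = 50% | 0% |
| 8 | 8/12 = 67% | 0% |

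The bias in a mean or a proportion is (K/12) × (stage effect), so 0.50 or 0.67 times that effect. It does not shrink with a larger trial. To illustrate with K = 6 and assumed R0 rates: 85% in resectable and 60% in borderline patients give a false gap of 0.50 × 25 = 12.5 points. With 80% and 70% it is 5 points, and with 90% and 50% it is 20 points.

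**Reading B.** With a fixed 12:12 split and no strata, the number x of borderline patients in one arm is hypergeometric: P(x) = C(K, x)·C(24−K, 12−x)/C(24, 12), with C(24, 12) = 2,704,156. The gap between arms is |2x − K|.

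For K = 6, a gap of 4 or more means x = 0, 1, 5 or 6: 2 × (18,564 + 190,944)/2,704,156 = 15.5%.

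Under simple randomisation x is binomial(K, ½). For K = 6 this gives 2 × (1 + 6)/64 = 21.9%.

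| K | P(gap ≥ 4), fixed 12:12 | P(gap ≥ 4), simple randomisation |
|---|---|---|
| 6 | 15.5% | 21.9% |
| 8 | 19.3% | 28.9% |
| 12 | 22.0% | 38.8% |

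**Effect on error rates under Reading B.** In 40,000 simulated null trials per scenario (unadjusted t-test at 0.05, fixed 12:12), overall type I error was 4.8% to 5.2%. Among trials with a gap of 4 or more it was about 6.6% to 6.8% if stage shifts the outcome by 0.5 SD, and 9.5% to 9.9% if by 1 SD (assumed effects).

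**After stratifying.** In permuted blocks of 4 (an illustrative size) within class, only an unfinished block can be unbalanced, and by 2 at most. The chance of a gap of 4 or more borderline patients is then 0.

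**The case against.** The strongest reply is that Reading B is the more natural one. The study is called randomised, every patient must be fit for either operation, and the allocation bullet precedes the borderline bullet and covers all patients. A laparoscopic operation begins with a laparoscope anyway, so only the open arm would need the extra step spelled out. The other borderline bullet names no arm, and nowhere do the documents say that borderline patients are assigned to open surgery. All of this stands. It makes Reading B at least as likely as Reading A, but no sentence states it.

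A reader might go further and infer that the trial compares tumour stage instead of approach. The documents do not support that. It would follow only under Reading A; under Reading B the imbalance is chance and overall type I error stays near 5%.

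A reader might also be struck that, with 6 borderline patients, a split of 4:2 or worse has a 64% chance. That is weak evidence. 4:2 is one patient away from balance, and with stratified blocks of 4 the last two of six patients fall in the same arm with probability 1/3, so 4:2 can still occur.

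Three further limits are fair:

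- The borderline features are listed with commas and joined by a conjunction that may require all of them. On a cumulative reading the class could be much rarer than 6 of 24.
- The R0 rates are illustrative, and 12.5 points is only 1.5 patients in 12. The proceed-or-abort decision would remove some advanced cases before resection.
- Not stratifying a very small single-centre trial is a defensible choice. That weakens the case for strata, but not the case for saying who is randomised.

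**Conclusion.** The concern holds in conditional form. The allocation bullet and the borderline bullet can be read against each other, and neither the inclusion criterion nor the rest of the protocol settles whether borderline patients are randomised.

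Under Reading A the confounding is systematic and large in proportion to whatever effect stage has. Under Reading B there is no systematic bias, only a material risk of a misleading chance imbalance: roughly one trial in five to seven with a fixed 12:12 split, and more often with simple randomisation. These sizes rest on the assumed borderline share. The conditional error rates also rest on an assumed stage effect. That the text is ambiguous rests on no assumption.

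This should be corrected before the allocation list is drawn up, because a site following the borderline bullet literally would break the randomisation for the most advanced cases.

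**What to change.** 1. Reconcile the two bullets under Methodology in details so that one statement says whether borderline patients are randomised. The borderline bullet should then be worded to agree with it. The staging procedure itself is for the investigators.
2. If they are randomised, allocate in small permuted blocks stratified by class (frank resectable versus borderline), using the class recorded before allocation and not revising it after intraoperative findings. In section 11, include class as a factor in the between-arm comparisons where event numbers allow. That should be feasible for operative time and blood loss, and may not be for rare events such as leakage.
3. If they are not randomised, say so in the eligibility criteria and exclude them from the randomised comparison.
4. Say whether the borderline features are all required or any one suffices, since this decides the size of the stratum.

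**Cost.** Some rewording and a second allocation list, with no new data and no more patients, because classification is already part of the work-up. The drawback is incomplete blocks in a small stratum. With 6 and 18 patients and blocks of 4, each stratum ends two patients into a block, so total arm sizes could reach 14:10, with probability 1/3 × 1/3 × 1/2 = 1/18. Excluding borderline patients would instead slow recruitment and narrow the population to which the result applies.
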